## **6.0 Subject Identification, Recruitment and Consent**

### **Discussion of Subject Population**

Patients that elect to have surgery typically require general anesthesia and tracheal intubation. Tracheal intubation is usually achieved, traditionally, by direct or indirect laryngoscopy, and is the preferred method when securing an airway. SGADs are the recommended alternative to laryngoscopy via laryngoscopes if failed or not possible, to aid in sufficient oxygenation and ventilation of patients according to difficult airway algorithms. Therefore, SGADs are constantly studied for significance and adequacy as a rescue device for emergent scenarios or when laryngoscopy fails.

### **Method Of Subject Identification And Recruitment**

Eligible subjects will receive a detailed explanation of the study, its purpose, their role, and study procedures in relation to what's considered research and standard of care (SOC); as well as the potential risks, benefits and alternatives prior to study enrollment. They will be given a consent form to read and if they so choose, to discuss with friends, family, and other clinicians. They will be invited to ask questions and, after all questions are answered to their satisfaction, invited to sign the consent form in accordance. The Principal Investigator (or delegate) will participate in the consenting process to ensure the subject has full understanding of the procedure and risks. No study-specific procedure will be performed before the consent form is signed.

### **Consent Process**

Eligible subjects will receive a detailed explanation of the study, its purpose, their role, and study procedures in relation to what's considered research and standard of care (SOC); as well as the potential risks, benefits and alternatives prior to study enrollment. They will be given a consent form to read and if they so choose, to discuss with friends, family, and other clinicians. They will be invited to ask questions and, after all questions are answered to their satisfaction, invited to sign the consent form in accordance. The Principal Investigator (or delegate) will participate in the consenting process to ensure the subject has full understanding of the procedure and risks. No study-specific procedure will be performed before the consent form is signed.

Subject participation in this investigation is voluntary. Written informed consent is required from all subjects prior to the subject's participation in the investigation. Also, an obtained permission of the faculty anesthesiologist, in charge of the patient's anesthesia care, must also be granted for subject participation. If the subject is illiterate or unable to adequately read the informed consent form, a witness' signature and a cross mark or a fingerprint of the subject is required. In accordance with FDA regulation 21 CFR Part 50, informed consent shall be obtained prior to any study procedure. The original of the signed consent

will be retained at the investigational site. A signed copy of the consent will be given to the subject. While not anticipated, Sponsor will report any failure to obtain subject consent to the IRB within 5 days of learning of such an event, as required by regulation.

Prior to participating in this investigation, the site will be required to have an IRB-approved Informed Consent Document. Any modifications to the consent must be approved by Sponsor and by the IRB of record. The Principal Investigator at each study site is responsible for obtaining and maintaining the approved informed consent and forwarding an IRB-stamped copy to Sponsor.

## 7.0 Criteria for Removal from the Study

Subjects may be withdrawn from the study for the following reasons:

- 1) Subject non-compliance with study procedures
- 2) Unacceptable adverse events (safety or tolerability)
- 3) The subject may withdraw from the study at any time and for any reason

Clinician decision that it is in the best interest of the subject to withdraw from the study

## 8.0 Study Intervention and Data Collection

This study involves the placement and usage of a laryngeal mask airway on a human subject for adequate airway management, oxygenation, and ventilation. The intervention directly related to this study is that of airway management, airway device/equipment, oxygen administration, mechanical ventilation, fiberoptic assistance, and tracheal intubation. The subject will have a surgical procedure that is incidental to his or her study participation, along with tracheal intubation. Besides the principal investigator and co-investigator, listed collaborators (anesthesiologists) will be involved in managing enrolled patient airways in accordance to the protocol. Randomization of the anesthesia practitioner is not necessary and will not occur. All patients will be recruited and enrolled based on the availability of the 8 study anesthesiologists during the study period.

### Patient Preparation Procedures

Prior to the surgical procedure, patient demographics and airway assessment will be recorded, as well as the selected randomized SGAD that will be used to secure the airway. The patient will be monitored with 5-lead ECG, pulse oximetry, non-invasive blood pressure (BP) and end-expiratory gas analysis. Vital sign measurements will be taken and recorded at the following time points: Pre-oxygenation, pre-induction, post-induction, post-SGAD insertion, 10 minutes after SGAD insertion, on admission to the post anesthesia recovery unit (PACU), and every 30 minutes until discharge from PACU. The patient will be positioned supine on the operating table with the head resting on a foam cushion and/or pillows and blankets (if needed). The patient will be pre-oxygenated via full facemask for a minimum of 3 minutes. Prior to pre-oxygenation, the circle system will be filled with 100% oxygen. The flow of oxygen will be set at 10 liters to obtain the highest end tidal concentration of oxygen (EtO2).

General anesthesia will be induced via traditional methods as requested by the anesthesiologist. Appropriate doses of propofol, fentanyl, and rocuronium will be administered as recommended by the anesthesiologist's discretion. A mixture of sevoflurane or desflurane will be utilized for maintenance of anesthesia. Vital signs will be recorded throughout. Lungs will be mechanically ventilated with a semi-closed circle system to maintain an end-tidal CO2 near 35mmHg. Once there are no twitches on the train of four (ToF) twitch monitor, following rocuronium administration, insertion of the randomized SGAD will then be performed. The size of the SGAD device used will be based on the manufacturers' recommendations or by clinical evaluation of the patient the anesthesiologist.

### SGAD Preparation Materials

The following materials will be ready on a preparation table before the anesthesia procedure is commenced: tablecloth, water-soluble lubricant, correct size of SGAD and one size bigger and one size smaller, 20 & 50 ml syringes, pressure gauge, silk tape for fixation of the SGAD, 16 Fr. gastric tube (max. size gastric tube recommended by the manufacturer – is listed in the CRF), 5 gauze wipes, and a timer.

### aScope Preparation Procedures

Prior to its use, the Ambu aScope3 Slim, and compatible Ambu aScope monitor, will be inspected for: visual harm to the scope, mechanical performance by tip manipulation, in which the distal end should be bent to a maximum in both directions while the scope is held in a straight position (The bending degree should be at least 110°), and aScope3 to aScope monitor connection. The quality of the monitors' standard installation should be evaluated. If the picture is not acceptable from the beginning, the quality will be adjusted via the contrast button and light button. When the picture quality is evaluated, the aScope3 Slim will be placed 1 cm from black letters placed on a white background to secure picture quality. When preparing the aScope3 Slim, the insertion cord should be well lubricated. When the aScope3 Slim has fulfilled the functional criteria, it should be placed on the preparation table and turned off. If flaws or errors are detected with the aScope3 Slim or the aScope monitor, either should be replaced and a new aScope3 evaluation will be performed with the new device. An alcohol wipe shall be used to thoroughly clean the lens if the image is not clear. Antifog should not be used for cleaning the aScope™ 3 Slim lens.

#### 1. Insertion of the SGAD

The patient will be placed in the sniffing position to optimize the oropharyngeal angle. The SGAD will be lubricated on the posterior surface of the cuff prior to insertion. Timing will begin when the tip of the cuff of the device touches the patient's lips. During insertion, the tip of the cuff will be pressed upwards against the hard palate and the cuff will be flattened against it. Jaw lift technique will be used on all patients. A jaw lift is performed by using the index finger and thumb of the non-dominant hand to lift the chin while the device is passed along the hard palate with the dominant hand. Additional maneuvers performed to optimize positioning or ventilation, such as adjusting head/neck position, additional jaw lift, adjusting depth of insertion, lateral insertion technique, or changing size of the SGAD. For the SGAD to be considered as placed correctly, the teeth of the patient should be between the teeth-marks indicated on the proximal end of the airway tube designed as a bite absorption area. The appearance of the first square end tidal carbon dioxide trace will indicate establishment of effective ventilation, and T1 (watch 1) will be stopped. Once successful placement has been confirmed, the cuff of SGAD will be inflated with air to attain an intra-cuff pressure of 60 cm H2O, measured with a handheld aneroid manometer (pressure gauge). The volume of air will be recorded. The SGAD will be taped to the participant's cheek with adhesive tape.

Unsuccessful appearance of CO2 curve suggests incomplete placement of the SGAD, and the device will be removed completely and another insertion attempt should be performed while the recording of time continues. An insertion attempt is defined as, when the SGAD touches the patient's lips. Only three attempts shall be made for proper device placement. The first two attempts will be made by either attending anesthesiologists or certified registered nurse anesthetists (CRNA) and the final attempt by the attending anesthesiologist. In case of failure of both SGAD and bag-mask ventilation, the airway will be secured according to the discretion of the attending anesthesiologist.

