### **2.0 Objectives and Hypothesis**

The purpose of this study is to estimate the ratio or difference in success rate of both the Ambu® AuraGain™ and Teleflex® LMA Protector™ during insertion and placement into an airway. Other findings include ease of supraglottic airway device (SGAD) insertion, anatomical fit of the SGAD (i.e. SGAD displacement, bloodstaining), rate of successful ventilation and intubation, functionality of gastric drainage channel (via orogastric tube insertion through each SGAD; to ensure easy insertion), oropharyngeal leak pressure (OLP; measured by a portable, handheld manometer), and postoperative complications in elective surgical patients who are not expected to have a difficult airway. Also, a fiberoptic assessment (with the Ambu® aScope™ 3 Slim) of the glottic view via the SGAD device and signs of airway morbidity will be investigated.

**2.1 Primary:** The ratio or difference in success rates of either the Ambu® AuraGain™ or Teleflex® LMA Protector™ during insertion and placement into an airway.

**2.2 Secondary:** Rate of successful ventilation and intubation (by utilizing the SGAD as an intubation conduit guided by the Ambu® aScope™ 3 Slim), ease of SGAD insertion (based on a numerical subjective rating scale), anatomical fit of SGAD (i.e. SGAD displacement, bloodstaining), OLP (measured by a portable, handheld manometer), functionality of gastric drainage channel which will be inserted through the appropriate channel of the SGAD, and postoperative complications

**2.3 Exploratory:** Fiberoptic assessment of the glottic view via the SGAD device and signs of airway morbidity

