### 11.0 Sample Size

The AMBU® AURAGAIN™ and TELEFLEX® LMA PROTECTOR™ are FDA approved SGADs that can be used for ventilation, and as a conduit for intubation. For patients in the general hospital setting, each device has exhibited a relatively high success rate of at least 90% as a ventilatory device. Success is defined as the insertion and placement of a SGAD on the first attempt. Success rates will be computed as proportions for each study arm. Taking the ratio of the success rates for each study arm will derive the relative risk. A two-sided 95% confidence interval will have the following lower and upper limits: (0.945, 1.255) assuming a relative risk of 1.089 (ie. success rate for study arm 1 = 0.90 and success rate for study arm 2 = 0.98) and 25 patients in each treatment arm.

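### Does listing a size change among the positioning manoeuvres leave first-attempt success open to two scorings?

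*Combined protocol and SAP*

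**What the plan says.** Section 2.1 states the primary objective as "The ratio or difference in success rates of either the" two devices during insertion and placement, without mentioning attempts. The working definition is in section 11.0: "Success is defined as the insertion and placement of a SGAD on the first attempt".

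Section 8.0, under Insertion of the SGAD, has four relevant elements:

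- **Counting rule:** "An insertion attempt is defined as, when the SGAD touches" the lips. At most three attempts are allowed.
- **Manoeuvres:** "Additional maneuvers performed to optimize positioning or ventilation" are listed, and the list ends with "adjusting depth of insertion, lateral insertion technique, or changing size of the SGAD". The sentence has no main verb and says nothing about counting.
- **Placement and ventilation:** correct placement is judged by where the teeth lie against the marks on the tube. Separately, "The appearance of the first square end tidal carbon dioxide trace will indicate establishment of effective ventilation", and the first timer stops.
- **No carbon dioxide curve:** "the device will be removed completely and another insertion attempt should be performed while the recording of time continues".

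The preparation list in section 8.0 has the next size up and the next size down on the table, so size changes are foreseen.

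**The concern.** Head position, jaw lift and depth can all be adjusted with the device in the mouth. A change of size cannot: one device comes out and another goes in. Placing it in the same list suggests that it belongs to the current attempt, whereas the lip-contact definition makes it a new one. If both readings were live, the same patient could be a success or a failure on the primary endpoint.

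A second worry concerns timing. The carbon dioxide trace comes before cuff inflation and leak testing. A device that gave a trace and was then exchanged for another size might be credited as a first-attempt success although it did not stay in place.

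With 25 patients per arm and success rates of 90% or more, a handful of such events could change the size or the direction of the estimate. The person inserting the device knows which one it is.

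**Working it through.** **1. Reproduce the plan's figure.** Inputs from section 11.0: success 0.90 (arm 1) and 0.98 (arm 2), 25 per arm, two-sided 95%.

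- Ratio = 0.98/0.90 = 1.0889.
- SE(ln ratio) = sqrt(0.10/(25 × 0.90) + 0.02/(25 × 0.98)) = 0.0725.
- Interval = exp(ln 1.0889 ± 1.96 × 0.0725) = (0.945, 1.255), as stated in the plan.

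**2. Weight of one patient.** 1/25 = 0.04, against a planning difference of 0.98 − 0.90 = 0.08. Expected failures: 25 × 0.10 + 25 × 0.02 = 2.5 + 0.5 = 3.0.

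**3. Effect if size changes were recoded.** The documents give no frequency, so 0 to 3 patients in one arm is an assumption. Starting from the planning rates, patients are moved from success to failure and the formula in step 1 is applied (arm 2 over arm 1):

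| Patients moved | In arm 2 only | In arm 1 only |
|---|---|---|
| 0 | 1.089 (0.945, 1.255) | 1.089 (0.945, 1.255) |
| 1 | 1.044 (0.887, 1.231) | 1.140 (0.964, 1.348) |
| 2 | 1.000 (0.831, 1.203) | 1.195 (0.986, 1.448) |
| 3 | 0.956 (0.778, 1.173) | 1.256 (1.013, 1.559) |

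One patient moved in each arm gives 1.093 (0.907, 1.317), close to the planned ratio.

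In whole counts, 23/25 v 24/25 gives 24/23 = 1.043 (0.907, 1.201). If both arm 1 failures were size changes and were recoded as successes, 25/25 v 24/25 gives 24/25 = 0.96. There SE = sqrt(0.04/24) = 0.0408, and the interval is about 0.89 to 1.04. The direction reverses, but both intervals include 1.

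**4. Does the text allow both scorings?** Take each case through the rules as written.

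- *Size changed because no trace appeared.* The device is removed completely and another attempt follows. This is attempt 2 on both the removal instruction and the lip-contact rule.
- *Size changed after a trace.* No sentence names this case. The replacement still reaches the lips, so it is attempt 2, and the device finally in place was not placed on the first attempt.
- *Position, lift or depth adjusted in place.* There is no new lip contact, so attempt 1 continues.

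The manoeuvre sentence changes none of these results. A step can serve to improve ventilation and also be a new attempt; the list gives the purpose and the definition gives the count. The intubation part of section 8.0 follows the same logic: once the tube has been withdrawn, the next try is a new attempt.

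**5. Is success fixed at the trace?** The trace marks effective ventilation and stops the timer. Placement has its own tooth-mark criterion, and section 11.0 requires placement as well as insertion. Nothing says that a device exchanged after a trace keeps its success.

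**The case for a change.** The strongest case for a change is that a primary endpoint this sensitive should not depend on inference. The first-attempt definition appears only in the sample-size section. Initial size may follow the manufacturer or clinical judgement, there are 8 study anesthesiologists, and nurse anesthetists may also make the first two attempts. One of them could read the manoeuvre list as permission to change size within an attempt. The exchange after a trace is not named anywhere, and a sentence settling it would cost almost nothing.

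Much of this is fair. The drafting is loose, the late exchange is unmentioned, and a clarifying sentence would do no harm. It does not show that the plan gives a wrong answer: the one rule that counts attempts gives a definite and sensible score in each case.

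The bias argument is weaker. No section says that the inserting operator decides how an attempt is scored. Section 14.0 has the investigator or a designee transfer source data to the case report form, and the sponsor compares the forms with source documents. The form itself (Appendix C) is not in the available text, so it may already record attempts and sizes.

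Requiring that the device stay unexchanged until the first leak-pressure reading would go beyond clarification. In the order of section 8.0 that reading follows the fiberoptic view and the gastric tube, so exchanges prompted by those steps would become insertion failures. Ventilation, anatomical fit and leak pressure are already secondary outcomes in section 2.2. That would be a different endpoint, on which reasonable statisticians could differ.

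**Conclusion.** No change to the plan is needed. A size change is a second lip contact, so it is a new attempt and not a first-attempt success. The manoeuvre list carries no competing scoring rule. What remains is a missing detail that analysts can fill by applying the stated definition in the same way to both arms, including to an exchange after the trace.

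The sensitivity is real: 4 points per patient, with two recoded patients in arm 2 enough to remove the planned difference. Any binary endpoint with 25 per arm has that sensitivity, and here it would arise only if the attempt rule were set aside. The illustrations rest on an assumed 0 to 3 size changes in one arm. The conclusion assumes that source records show each insertion and the size used, and that the case report form contains no contrary rule.

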### 10.0 Statistical Methods

Descriptive statistics such as the mean (standard deviation) or median (range) will be used to summarize continuous variables as appropriate. Frequencies and percentages will be used to summarize categorical variables, such as success rates. Independent samples t-tests or Wilcoxon rank-sum tests (if more appropriate) will be used to compare differences in continuous variables between study arms. Fisher's exact test or Chi Square test will be used to compare categorical variables between study arms. Correlations and regression will be used to estimate associations of interest, primarily for exploratory analyses and further hypothesis generation.

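### Fixed blocks of 2, printed in the protocol of a trial with no described blinding, let up to 25 of 50 allocations be deduced; undisclosed mixed blocks, set before enrollment, would reduce this cheaply

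*Combined protocol and SAP*

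**What the plan says.** **Allocation.** Section 5.0 (Randomization) names CORe as the randomization software and sets 25 blocks, each of two patients, for the two devices. It gives no stratification factor. No section describes blinding or says how upcoming assignments are kept from staff.

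**When the device is known.** Under Patient Preparation Procedures (Section 8.0), the items recorded before surgery include the demographics and airway assessment, "as well as the selected randomized SGAD that will be used to secure the airway". Insertion of the SGAD then has staff lubricate, insert and inflate that device.

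**Who makes the scored attempt.** Section 11.0 defines the endpoint: "Success is defined as the insertion and placement of a SGAD on the first attempt". On operators, Insertion of the SGAD says "The first two attempts will be made by either attending anesthesiologists or certified registered nurse anesthetists (CRNA"); only the final attempt is reserved for the attending. Section 8.0 adds "Randomization of the anesthesia practitioner is not necessary and will not occur" and "All patients will be recruited and enrolled based on the availability of the 8 study anesthesiologists during the study period". The Consent Process requires "an obtained permission of the faculty anesthesiologist, in charge of the patient's anesthesia care", so the attending is tied to the patient. What is left open is attending or CRNA within that team.

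**Aim and analysis.** Section 2.0 states "The purpose of this study is to estimate the ratio or difference in success rate". Section 10.0 compares the arms without an operator term: "Fisher's exact test or Chi Square test will be used to compare categorical variables between study arms".

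**The concern.** A block of two is the shortest possible 1:1 block. Once its first allocation is known, the second is fixed. Here the block size is in the protocol and the assigned device is in plain sight, so the deduction needs no access to the randomization list. Someone who can deduce the next device could, knowingly or not, let it influence whether or when a borderline candidate is enrolled, or who is lined up for the first attempt. Randomization protects the comparison only if those decisions are made without knowledge of the assignment.

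The operator question is related but secondary. The endpoint is scored on one attempt, two types of staff may make it, and no rule says when that is settled. If the choice followed the device and the two types differed in success, the estimated ratio or difference would shift, and the confidence interval would not show it. The two matters meet at one point: naming the operator before the assignment is opened protects little if the assignment can already be deduced.

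**Working it through.** **1. The plan's own figure.** Inputs from Section 11.0: success rates 0.90 and 0.98, 25 patients per arm, two-sided 95% interval.

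- RR = 0.98/0.90 = 1.089.
- SE(log RR) = sqrt(0.10/(25×0.90) + 0.02/(25×0.98)) = 0.0725.
- Interval = 1.089 × exp(±1.96×0.0725) = (0.945, 1.255), as stated.

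Nothing below changes this interval or the total of 50.

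**2. Allocations known with certainty.** In a block of known size 2m, the expected number of allocations forced by the earlier ones is 2m/(m+1).

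- Blocks of 2: 1 per block, so 25×1 = 25 of 50.
- Five blocks of 4 and five of 6 (5×4 + 5×6 = 50), order undisclosed: about 4.4 of 50 on average. This is by simulation, for an observer who sees every earlier allocation and knows there are five of each size.
- The same ten blocks with the order disclosed: 5×4/3 + 5×6/4 = 14.2 of 50. Most of the gain therefore depends on keeping the order hidden.

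**3. Best guesses.** The best strategy is to guess the arm that is behind. Expected correct guesses per block of 2m are m + (4^m/C(2m,m) − 1)/2.

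- Block of 2: 1 + (4/2 − 1)/2 = 1.5. Over 25 blocks: 37.5 of 50, or 75%.
- Block of 4: 2 + (16/6 − 1)/2 = 2.833. Block of 6: 3 + (64/20 − 1)/2 = 4.1. Together: 5×2.833 + 5×4.1 = 34.7 of 50, or 69%.

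Pure chance is 50%. The gain is mainly the loss of certainty, not of predictability.

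**4. Cost in balance.** If enrollment stops mid-block, the largest arm difference is half the block: 1 with blocks of 2, 3 with a block of 6.

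**5. Size of an operator effect (assumptions only).** The documents give no success rate by operator type and no CRNA share. Take the two devices as identical. Then the spurious difference = (attending rate − CRNA rate) × (difference between arms in CRNA share).

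| Assumed CRNA split by arm | Operator gap | Spurious difference |
|---|---|---|
| 40/60 | 5 points | 0.05×0.20 = 1 point |
| 40/60 | 10 points | 0.10×0.20 = 2 points |
| 20/80 (extreme) | 10 points | 0.10×0.60 = 6 points |

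For comparison, the planned 95% half-width on the difference scale is 1.96 × sqrt(0.90×0.10/25 + 0.98×0.02/25) = 1.96×0.0662 = 0.130, or 13 points. If the choice is unrelated to the device, only chance imbalance remains. With a 50% CRNA share and a 10-point gap, its SD is sqrt(2×0.5×0.5/25)×0.10 = 0.014, or 1.4 points.

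By exact enumeration with 25 per arm, Fisher's test rejects 0.9% of the time with no shift (0.90 in both arms), 1.1% at 2 points (0.91 against 0.89) and 2.8% at 6 points (0.93 against 0.87). The uncorrected chi-square test rejects 4.9%, 5.5% and 10.4%. With about 2.5 failures expected per arm, Fisher's is the more suitable of the two.

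**The case against.** **CORe may conceal the list.** It may, and the documents do not say either way. Hiding the list does not help, however, when the second allocation follows from the first and the block size is printed.

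**The figure of 25 needs someone who sees everything.** This stands as a limit. If only the treating anesthesiologist saw each allocation, and the 8 shared cases equally and independently (an assumption), about 25/8 = 3 second allocations would be deducible. A coordinator who sees every allocation brings the number back to 25.

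**The remedy gains little.** In part this stands: 69% correct guesses is still well above chance. Also, replacing the list is simple only before the first patient is randomized. Afterwards it would mean changing the list mid-trial.

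**The operator point is speculative.** This largely stands. The documents do not say when the operator is chosen, and recording the device before surgery fits a team that is already in place. The protocol explicitly judges that practitioners need not be randomized. Section 17.0 requires training of the investigators on both devices, one jaw-lift technique is set for all patients, and Section 10.0 allows exploratory regression. Appendix C, the case report form, is not in the text and may already record the operator. None of this fixes the order of events, but it is a reason to keep the point secondary.

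**Conclusion.** The block-size point holds as a low-cost improvement. Fixed, published blocks of 2 make up to 25 of 50 allocations certain to anyone who sees every earlier one. Undisclosed mixed blocks cut that to about 4.4, with a modest fall in the best-guess rate from 75% to 69%. The count of 25 assumes full sight of earlier allocations. The documents give no basis for putting a size on any resulting selection effect on the success rates.

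Two stronger readings are tempting, and the documents support neither.

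- A reader might infer that staff do anticipate assignments or select patients by them. The text shows only that they could.
- A reader might infer that the operator is chosen to suit the device and that the primary comparison is therefore biased. That needs both a device-driven choice and a success gap between attendings and CRNAs, and the documents show neither. What can be said is that no rule prevents such a choice. In the moderate case the shift is 1 to 2 points against a 13-point half-width; 6 points needs an extreme split.

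**What to change.** **Main change, before enrollment starts.** In Section 5.0, replace the 25 blocks of 2 with randomly ordered blocks of undisclosed size, for example five of 4 and five of 6, which keeps 25 per arm. Remove the block size from the protocol given to enrolling staff and hold it in a document kept by whoever generates the list. The cost is one regenerated list and a possible imbalance of 3 instead of 1 if enrollment stops mid-block. Sample size and planned interval stay as they are.

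**Optional addition.** Under Insertion of the SGAD, add wording such as: *The person intended to make the first attempt, and whether attending or CRNA, is recorded before the assignment is opened. Any later change is recorded with its reason.* This is one entry per patient, possibly already on the case report form, with slightly less freedom in rostering. It does not ask for practitioners to be randomized. An operator-adjusted estimate is not proposed: the Section 11.0 scenario expects only 25×0.10 + 25×0.02 = 3 failures in all.
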